3.1.3 Definition of Baseline

Baseline is defined as the last measurement prior to the first dose of study drug, unless otherwise stated.

Liver tests (Alanine aminotransferase, Aspartate aminotransferase, and total bilirubin) baseline values are determined by averaging the values obtained at screening visits 1 and 2 to obtain the arithmetic mean.

UPCR and eGFR baseline values are defined as the geometric mean of 2 assessments prior to randomization.

3.1.4 Change and Percent Change from Baseline

Change from baseline will be derived as visit value minus baseline value. Percent change from baseline will be defined as [(visit value minus baseline value) divided by baseline value] multiplied by 100. In case where baseline value equal 0, baseline value of 0.001 will be used to calculate percent change from baseline.

3.1.5 Summary Statistics

Categorical data will generally be summarized with counts and percentages of patients. The denominator used for the percentage calculation will be clearly defined. Continuous data will generally be summarized with descriptive statistics including n (number of non-missing values), mean, median, standard deviation, minimum, and maximum.

3.1.6 Hypothesis Testing

No formal hypothesis testing will be conducted.

3.1.7 Evaluation of Site Effect

The number of patients at each site is expected to be small. Site effect will not be considered.

3.1.8 Handling of Dropouts and Missing Data

Date Values

In cases of incomplete dates (e.g., AE, concomitant medication, and medical history start and/or stop dates), the missing component(s) will be assumed as the most conservative value possible. For example, if the start date is incomplete, the first day of the month will be imputed for the missing day and January will be imputed for the missing month. If a stop date is incomplete, the last day of the month will be imputed for the missing day and December will be imputed for the missing month. If it is not possible to determine whether an AE is or is not treatment emergent due to completely or partially missing dates, the dates will be imputed in a conservative way so that the AE will be considered as treatment emergent, i.e., starting in the on-treatment period. Incomplete start and stop dates will be listed as collected without imputation.

In cases of incomplete date for Alport syndrome genetic testing or Alport diagnosis, the 15th day of the month will be imputed for missing day and June will be imputed for missing month.

Date imputation will only be used for computational purposes such as treatment-emergent status. Actual date values, as they appear in the original CRFs, will be presented within the data listings.

Non-Date Values

For the secondary endpoint, to assess the effect of setanaxib on eGFR compared to placebo, missing values will be imputed using multiple imputation methods (see Section 3.5.1). For the analyses of all other endpoints, no imputation will be made for missing values. Safety data will be used according to availability, with no imputation for missing data.

3.1.9 Laboratory Values Above or Below Limits of Quantification

For continuous laboratory values less than the lower limit of quantification (LLQ), half of the lower limit value (i.e. LLQ/2) will be used in the analysis. For values greater than the upper limit of quantification (ULQ), the upper limit value (i.e. ULQ) will be used in the analysis.

3.2 Analysis Populations

3.2.1 Full Analysis Set (FAS)

The Full Analysis Set (FAS) will include all patients who are randomized into the study.

3.2.2 *Safety Analysis Set (SAS)*

The Safety Analysis Set (SAS) is defined as all randomized patients who take at least 1 dose of the study drug.

3.2.3 *Pharmacokinetic (PK) Analysis Set*

The Pharmacokinetic Analysis Set will be defined as all randomized patients who take at least 1 dose of the study drug and have at least one measured concentration, including any BQL, at a scheduled PK time point post-dose.

3.3 Patient Data and Study Conduct

3.3.1 *Patient Disposition*

Counts and percentages of patients who were screened (signed informed consent), discontinued early during screening (screen failures), randomized and received at least one dose of study drug will be summarized in total based on all screened patients. Reasons for early discontinuation will also be summarized.

Counts and percentages of patients who were randomized, received at least one dose of study drug, discontinued early from the study, and completed the study will be summarized by treatment and in total based on all randomized patients. Reasons for early discontinuation will also be summarized.

3.3.2 *Protocol Deviations*

Protocol deviations will be identified based on clinical data as defined in the Protocol Deviation Plan, where all protocol deviations will be defined as either CSR reportable or non-CSR reportable. The CSR reportable protocol deviations will be categorized and separated by treatment group. The CSR reportable deviations will include all randomized patients using counts and percentages.

3.3.3 *Analysis Populations*

Counts and percentages of patients in each analysis population will be summarized by treatment and in total based on all randomized patients. Reasons for exclusion from each analysis population will also be summarized.

3.3.4 *Demographic and Baseline Characteristics*

The following demographic and baseline characteristics will be summarized with descriptive statistics or counts and percentages of patients as appropriate by treatment and overall, for the FAS:

- Age (years) and age categories (12 to 17, ≥ 18 years) at the time of consent
- Sex
- Childbearing potential
- Race
- Ethnicity
- Height (cm)
- Weight (kg)
- Body mass index (BMI) (kg/m^2) and BMI categories ($<30 \text{ kg}/\text{m}^2$, $\geq 30 \text{ kg}/\text{m}^2$)

- Time since genetic diagnosis
- Gene and inheritance pattern
- Time since clinical diagnosis.

3.3.5 Medical History

Medical history will be coded to system organ class and preferred term using the Medical Dictionary for Regulatory Activities (MedDRA) version v26.1. Counts and percentages of patients with medical history by system organ class (SOC) and preferred term (PT) will be summarized by treatment group and in total based on randomized patients.

3.3.6 Prior and Concomitant Medications

Prior and concomitant medications will be coded to anatomical therapeutic chemical (ATC) class and preferred term using the WHO Drug Dictionary version March 2023. For summary purposes, medications will be considered prior medications if they stopped prior to the first dose of study drug and concomitant medications if they were taken at any time after the first dose of study drug (i.e., started prior to the first dose of study drug and were ongoing or started after the first dose of study drug). Counts and percentages of patients taking prior and concomitant medications by ATC class and preferred term will be summarized by treatment group and in total based on the SAS.

3.3.7 Study Drug Exposure and Compliance

Days of exposure to study drug will be calculated as date of last dose of study drug – date of first dose of study drug + 1. Note that the exposure calculation is intended to describe the length of time a patient was exposed to study drug and therefore does not take study drug interruptions into account. Days of exposure to study drug will be summarized by treatment group based on the SAS with descriptive statistics and with counts and percentages of patients with exposure in the following categories:

- <4 weeks
- 4 - <8 weeks
- 8 - <12 weeks
- 12 - <16 weeks
- 16 - <18 weeks
- 18 - <24 weeks
- ≥24 weeks

Percent compliance to the study drug will be calculated using the following formula:

$$\frac{\# \text{ tablets dispensed} - \# \text{ tablets returned}}{\# \text{ expected tablets taken}} \times 100$$

If study drug is not returned, the number of tablets returned will be considered 0 for the compliance calculation. The expected tablets taken will be calculated as the earliest date between the end of treatment date and the date of early termination – the date of first dose +1 (multiply by 3 if patient 12 to 17 years old and multiply by 4 if patient ≥18 years old).

Percent compliance to the study drug will be summarized by treatment group based on the SAS with descriptive statistics and with counts and percentages of patients with compliance in the following categories:

- <80%
- 80-120%
- >120%

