5.6 Drug Supplies

5.6.1 Formulation and Packaging

Setanaxib film-coated tablets contain 400 mg setanaxib formulated with excipients and will be provided in high-density polyethylene (HDPE) bottles.

Matching film-coated placebo tablets, containing only excipients, will also be provided in HDPE bottles.

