5.6.4 Treatment Compliance

Patients will be instructed to return all empty bottles and unused study drug to the site at the study visits indicated in [Appendix A](#). Patients will return all remaining unused study drug at Study

Visit 8. Treatment compliance will be assessed at each study visit after baseline (Day 1) through Week 24.

Accountability of the used and unused study drug will be recorded. Compliance with the study drug regimen will be evaluated by counting unused tablets. During the Treatment Period, if compliance is not between 80% and 120%, inclusive, the patient will be counseled about the importance of compliance with the study drug regimen.

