8.8.1 Detection and Management of Potential Bone Marrow Toxicity

Particular attention will be given to the detection and management of potential cases of bone marrow toxicity. In case of Grade ≥ 2 severity anemia, the Investigator will instruct the patient to interrupt IMP administration and to return to the study site within 7 days so that the absolute reticulocyte count can be retested. If the retest value is below 50% of the baseline value (Screening Study Visit 2), IMP will not be resumed and will be permanently discontinued. IMP administration will be resumed only if the retest value of the absolute reticulocyte count is $\geq 50\%$ of the baseline value and a Grade ≤ 1 of anemia, and an alternative cause for the anemia can be documented. The patient will continue to be closely monitored (at least weekly) until normalization of the reticulocyte count, ie, return to baseline values.

Anemia will be reported to the Sponsor (or designee) as an AESI, as defined in [Section 8.1.4](#), following the same procedure as for SAEs ([Section 8.3](#)).

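### Unreturned tablets are scored as taken, so a patient who leaves with the last supply gets a compliance figure that no tablet count supports

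*SAP*

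**What the plan says.** SAP 3.3.7 defines percent compliance as tablets dispensed minus tablets returned, over tablets expected. For the numerator it adds: "If study drug is not returned, the number of tablets returned will be considered 0 for the compliance calculation". The denominator is a number of calendar days times tablets per day. The days run from first dose to "the earliest date between the end of treatment date and the date of early termination", and the daily count is set by age: "multiply by 3 if patient 12 to 17 years old and multiply by 4 if patient ≥18 years old". The result is summarized by arm on the Safety Analysis Set, with descriptive statistics and three categories: below 80%, 80 to 120%, and above 120%.

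Protocol 5.6.4 describes the measurement behind this: "Compliance with the study drug regimen will be evaluated by counting unused tablets". It also has patients bring back empty bottles. A bottle returned empty (intake known) can therefore be told apart from a bottle never returned (intake unknown).

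Neither document defines the end of treatment date or says how the early termination date is set for a patient lost to follow-up. SAP 3.3.7 says that its exposure figure "does not take study drug interruptions into account". The compliance text does not mention interruptions, and its denominator deducts none.

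**The concern.** The rule fills a missing count with the largest possible intake, while the denominator is cut off when the patient leaves. The two halves of the ratio then cover different periods: a supply meant for the coming weeks is set against days that have already passed. The patients affected are those who leave without an accountability visit, whose intake is least known.

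Compliance is one of the first things a reader checks when a treatment effect on UPCR looks weak or an adverse event needs context, and this trial is meant to inform the design of later studies. With about 18 patients, a single artificial value is visible in an arm's mean and category counts.

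**Working it through.** **Inputs.** Tablet strength: "Setanaxib film-coated tablets contain 400 mg setanaxib" (Protocol 5.6.1). Daily doses are 1200 mg (12 to 17 years) and 1600 mg (18 years and over) (Protocol 5.1.1). Dispensing is at Visits 3, 5, 6 and 7, that is Days 1, 43, 85 and 127 by the target days in SAP 3.1.2; Week 24 is Day 169. The number of tablets per dispensing is not stated. I assume 42 days of dosing, with 49 days for the last supply as a variant that covers the +7-day visit window.

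**The plan's own multipliers.** 1200/400 = 3 and 1600/400 = 4 tablets per day, as in SAP 3.3.7. Since tablets per day cancel, the percentages below hold for both age groups.

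**Last supply not returned.** Suppose earlier supplies were used up and returned empty. With k supplies dispensed and termination dated Day D, compliance = 42k / D. No drug is dispensed at Week 2, so that row assumes the first supply went home again and did not come back.

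| Last attended visit | k | Dated at that visit | Dated at next missed visit |
|---|---|---|---|
| Week 2 (Day 15) | 1 | 42/15 = 280% | 42/43 = 97.7% |
| Week 6 (Day 43) | 2 | 84/43 = 195% | 84/85 = 98.8% |
| Week 12 (Day 85) | 3 | 126/85 = 148% | 126/127 = 99.2% |
| Week 18 (Day 127) | 4 | 168/127 = 132% | 168/169 = 99.4% |

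With a 49-day last supply, the middle column becomes 49/15 = 327%, 91/43 = 212%, 133/85 = 156% and 175/127 = 138%.

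**When the value exceeds 120%.** 42k/D > 1.2 means D < 35k, so D is at most 34, 69, 104 or 139. That is within 33, 26, 19 or 12 days of the last dispensing.

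**Why the 98 to 99% figures are also unsupported.** For a patient last seen at Week 6 and dated Day 85, the rule gives 84/85 = 98.8%. If none of the second supply was taken, the true value is 42/85 = 49.4%. The data cannot separate the two. Counting only the interval with a return (Days 1 to 42) gives 42/42 = 100% for that interval and claims nothing about the rest.

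**Weight of one patient.** At 18 patients and 2:1, the arms are 12 and 6: 1/12 = 8.3% and 1/6 = 16.7%. One 280% value among five at 100% gives a mean of (280 + 500)/6 = 130%; the median stays at 100%.

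**Undefined end of treatment date.** Protocol 4.3 lets a patient stop study drug and stay in the study. Take an adult who takes every tablet to Day 60, stops, and returns the remainder. If the end date is the last dose, compliance is 240/240 = 100%. If it is the Week 24 visit, which SAP 3.1.2 labels EOT, it is 240/(4 × 169) = 35.5%.

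**Directed interruptions.** Under Protocol 8.8.1, for Grade 2 or higher anemia, "the Investigator will instruct the patient to interrupt IMP administration and to return to the study site within 7 days". With 168 days and I days off, compliance = (168 − I)/168: 95.8% for 7 days, 83.3% for 28 and 79.8% for 34. Over a full course, 34 days is the shortest interruption that falls below 80%.

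**The case against.** The strongest reply is that nothing depends on this figure. No analysis set uses compliance, it enters neither the UPCR nor the eGFR model, and there is no formal hypothesis test. SAP 3.3.7 also tabulates days of exposure in seven categories, so an early stopper shows there whatever the compliance value. Disposition, patient listings and plasma concentrations at Weeks 2, 12 and 24 add further evidence. Withdrawn patients should have an early termination visit where possible, with the Visit 8 procedures including drug return, so an unreturned supply is a residual case. All of this stands and limits the importance of the point. It does not make the compliance figure right when the case occurs.

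Three stronger readings are tempting, and the documents do not support them:

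- A reader might infer that patients lost to follow-up will be classed as overdosed. Protocol 8.7 requires that extra intake be clear, or suspected by the investigator; an accountability discrepancy alone is not enough.
- A reader might infer that such patients always land above 120%. Under the 42-day assumption that needs a termination date within 12 to 33 days of the last dispensing, depending on the interval. A later date puts them inside 80 to 120%.
- A reader might infer that patients who follow an interruption instruction are scored as non-compliant. A 7-day interruption over 24 weeks costs about 4 points. Protocol 8.8.1 sets no maximum length, so a longer one is possible, but no figure in the documents suggests that 34 days is typical. Whether directed interruptions belong in the denominator is a reporting choice.

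**Conclusion.** The point holds in a limited form. As written, the SAP rule reports unknown intake as full intake whenever the last supply is not returned. Assuming 42-day supplies and full use of earlier ones, the reported value is 132% to 280% or about 98% to 99%, and the difference comes only from how the termination date is recorded, which the documents leave open. The lower figures do as much harm as the higher ones, because they look like good compliance.

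The undefined end of treatment date is a separate ambiguity in the same calculation: 100% or 35.5% for the same patient stopping on Day 60.

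The consequence is a misleading descriptive table, with no effect on any endpoint, analysis set or overdose determination. It is worth correcting because the arms are small and the change is cheap.

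**What to change.** Replace the sentence on unreturned drug in SAP 3.3.7. For a dispensing interval whose supply is not returned, treat the count as missing and leave that interval out of both numerator and denominator. Report the numbers of patients and intervals affected by arm, and add a sensitivity row with two bounds: all of the unreturned supply taken, and none of it taken.

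In the same edit, define the end of treatment date for this calculation as the date of last dose. Optionally, show compliance a second time with documented protocol-directed interruption days removed from the denominator.

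The cost is a few sentences of SAP text before database lock and minor programming, with no change to conduct or data collection. There are two drawbacks. Some patients will have compliance based on fewer intervals, and a patient lost in the first interval will have none, so without the bounds the main summary would omit those whose intake is least known. And with the denominator ending at last dose, early stopping no longer lowers compliance; it must be read from the exposure table.

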3.4 Safety Assessment

The SAS will be the primary population for the safety analysis.

3.4.1 Adverse Events -Primary Endpoint

The primary endpoints are:

- Percentage of patients with treatment-emergent SAEs;
- Percentage of patients with treatment-emergent AESIs.

All adverse events (AEs) will be coded to SOC and PT using MedDRA version v 26.1. Treatment-emergent adverse events (TEAEs) are defined as AEs that start after the first dose of study drug and up to 30 days post-last dose of study drug. Pre-treatment AEs are defined as AEs that started prior the first dose of study drug and post-treatment AEs are defined AEs that started more than 30 days after last dose of study drug.

AESI is defined as CTCAE Grade ≥ 2 anemia, defined as hemoglobin <10g/dL, and absolute reticulocyte counts of <50% of the baseline value (Screening Study Visit 2), which are confirmed by repeat testing.

Estimand

To assess the primary endpoint for treatment-emergent SAE, the safety estimand is defined by the following key attributes, according to the framework provided in International council for Harmonization (ICH) E9 (R1) [1]:

- **Treatment:** Setanaxib treated patients compared to placebo
- **Population:** The SAS comprised of all randomized patients who took at least 1 dose of the study drug.
- **Variable of interest:** Treatment-emergent SAEs
- **Intercurrent event handling:** All events will be counted regardless of early discontinuation of treatment, up to 30 days post-last dose of study drug
- **Summary measures:** Count and percentage of patients experiencing SAEs during the Treatment Period up to 30 days post-final dose.

The number and percentage of patients with SAEs will be presented by treatment group, system organ class (SOC), and preferred term (PT). Similar summaries will be presented for treatment emergent AESIs. The number and percentage of patients with study drug related treatment-emergent SAEs and AESIs will be presented by treatment group, SOC and PT.

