8.1 Adverse Events

An AE is defined as any untoward medical occurrence in a patient administered a pharmaceutical product, which does not necessarily have a causal relationship with this treatment. An AE can therefore be any unfavorable and/or unintended sign (including a clinically significant abnormal laboratory finding), symptom, or disease temporally associated with the use of an IMP, whether or not related to the IMP. All AEs, including observed or volunteered problems, complaints, or symptoms, are to be recorded on the appropriate eCRF. The Investigator should update the appropriate eCRF if additional follow-up information becomes available (eg, the AE has subsided, stabilizes, or the condition becomes chronic in nature).

AEs, which include clinical laboratory test results, will be monitored and documented from the time of informed consent/assent until the end of the Follow-up Period (Study Visit 9). Patients should be instructed to report any event that they experience to the Investigator, whether or not they think the event is due to study drug. From the time of informed consent/assent, Investigators should make an assessment for AEs at each visit and record the event on the appropriate AE eCRF.

Wherever possible, a specific disease or syndrome rather than individual associated signs and symptoms should be identified by the Investigator and recorded on the eCRF. However, if an observed or reported sign or symptom is not considered a component of a specific disease or syndrome by the Investigator, it should be recorded as a separate AE on the eCRF. Additionally, the condition that led to a medical or surgical procedure (eg, surgery, endoscopy, tooth extraction, or transfusion) should be recorded as an AE, not the procedure itself.

Any medical condition already present at informed consent/assent should be recorded as medical history and not be reported as an AE unless the medical condition or signs or symptoms present at baseline change in severity, frequency, or seriousness at any time during the study. In this case, it should be reported as an AE.

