9.2.1 Analysis of Safety

To assess the primary objective, the primary safety estimand for SAE is defined by the following key attributes, according to the framework provided in International Council for Harmonisation (ICH) E9 (R1):

Treatment: Setanaxib treated patients compared to placebo.

Population: The SAS comprised of all randomized patients who took at least 1 dose of the study drug.

Variable of interest: SAEs.

Intercurrent event handling: All events will be counted regardless of early discontinuation of treatment, up to 30 days post-last dose of study drug.

Summary measure: Count and percentage of patients experiencing SAEs during the Treatment Period up to 30 days post-final dose.

The analysis of the primary endpoint will be performed using the SAS. The number and percentages of patients with SAEs and treatment-emergent AESIs will be presented by treatment group, system organ class, and preferred term. Additional summaries of AEs, TEAEs, AEs leading to discontinuation of study treatment, and AEs by severity, seriousness, and relationship to study drug(s) will be presented.

Clinical laboratory parameters, vital signs, ECGs, thyroid, hearing and physical examinations will be summarized by treatment group by visit. Change from baseline values by visit will be presented for the continuous parameters. The count (and percentage) of patients with clinically significant changes will be tabulated by treatment group.

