6 CHANGES FROM PROTOCOL-SPECIFIED STATISTICAL ANALYSES

There have been two changes from the protocol v3.0:

The first change is the clarification of the primary endpoint: only treatment-emergent serious adverse events will be included in the analysis of the primary endpoint.

The second change is the inclusion of MMRM analysis for the ratio of eGFR at 24 weeks compared to baseline, if the model convergence, from multiple imputation approach, is questionable and the given parameter estimates cannot be obtained.

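### SAP 3.4.1 decides treatment-emergence by start date alone, so an AE that begins before the first dose and becomes serious on study drug falls outside the primary SAE endpoint, against the SAP's own summary measure

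*SAP*

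**What the plan says.** SAP 3.4.1 gives two complementary definitions. The first is "Treatment-emergent adverse events (TEAEs) are defined as AEs that start after the first dose of study drug and up to 30 days post-last dose". The second is "Pre-treatment AEs are defined as AEs that started prior the first dose of study drug". Neither mentions a change in severity or seriousness after dosing.

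Both primary endpoints use the first definition. SAP Section 6 records, as a change from the protocol, that "only treatment-emergent serious adverse events will be included in the analysis of the primary endpoint". The other primary endpoint is "Percentage of patients with treatment-emergent AESIs", which was already limited to treatment-emergent events in Protocol Section 2.

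The estimand wording differs. The summary measure in SAP 3.4.1 is "Count and percentage of patients experiencing SAEs during the Treatment Period up to 30 days post-final dose", with no condition on when the AE began, and Protocol 9.2.1 gives "Variable of interest: SAEs". The sentence in SAP 3.4.1 on presenting the results also refers to SAEs without the treatment-emergent limit.

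On collection, Protocol 8.1 states that AEs "will be monitored and documented from the time of informed consent/assent until the end of the Follow-up Period". Events that begin during screening therefore exist as AE records with a pre-dose start date.

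**The concern.** Safety is the primary objective, and deterioration on study drug is what the primary endpoint should pick up. Under the start-date rule, two patients with the same on-treatment course can be classified differently because of when a mild precursor was first noted.

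The rule reaches beyond the primary endpoint. The SAP 3.4.2 tables of TEAEs by severity, Grade 3 or above, relatedness and discontinuation all use it. SAP 3.4.3 identifies clinically significant laboratory changes through TEAEs, so a named safety endpoint inherits the same gap.

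Because the estimand wording points the other way, two programmers working from SAP 3.4.1 could produce different primary results.

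**Working it through.** The documents state no event rate, power or error rate for this endpoint, so there is no planned figure to reproduce. The check is a comparison of wordings, followed by the scale of one misclassification.

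**1. Four cases under the two wordings in SAP 3.4.1**

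- *AE starts after first dose and is serious:* counted by the TEAE definition and by the summary measure.
- *AE starts in screening and becomes serious on drug:* pre-treatment under the TEAE definition, so not counted. Counted by the summary measure.
- *SAE starts and resolves in screening:* counted by neither.
- *Condition present before consent that worsens on drug:* Protocol 8.1 makes the worsening reportable as an AE. If that AE is dated at the worsening, both wordings count it.

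The conflict is confined to the second case.

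**2. Do the recording rules close the gap?**

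The worsening rule in Protocol 8.1 is written for conditions already present at consent and held as medical history. For an AE already on record, Protocol 8.1 tells the investigator to update the eCRF, and 8.3.2 puts new information in the form first completed. Neither section asks for a new record with a new start date. The conservative date imputation in SAP 3.1.8 helps only where dates are missing or partial.

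**3. Length of the exposed period**

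Inputs: screening of 4 weeks ±7 days (Protocol Table 2, footnote e); Visit 3 within 10 (+3) days after randomization (Protocol 5.4).

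- Nominal: 28 + 10 = 38 days.
- Outer windows: (28 + 7) + (10 + 3) = 35 + 13 = 48 days.
- Longer if genetic test results are awaited.

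For comparison, the treatment-emergent period is 168 + 30 = 198 days.

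**4. Effect of one patient**

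Inputs: about 18 patients, maximum 20 (Protocol 9.2.3); 2:1 allocation. The change in an arm's percentage is 100/n.

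- N = 18: setanaxib 100/12 = 8.3 points; placebo 100/6 = 16.7 points.
- N = 20, assuming a 13:7 split: 100/13 = 7.7 points; 100/7 = 14.3 points.

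The shift occurs only if the patient has no other qualifying SAE.

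**5. Chance of at least one affected patient**

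The proportion p of patients with a screening-onset AE that worsens on drug is not given, so the values below are assumptions. The formula is 1 − (1 − p)^N.

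| Assumed p | N = 18 | N = 20 |
|---|---|---|
| 1% | 16.5% | 18.2% |
| 2% | 30.5% | 33.2% |
| 5% | 60.3% | 64.2% |
| 10% | 85.0% | 87.8% |

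These figures concern worsening of any kind. An AE that goes on to become serious is a narrower event, so for the primary SAE endpoint p would be no larger than this and could be much smaller.

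**The case against.** The strongest reply is that SAP 3.4.1 does not clearly exclude the event. The summary measure and the presentation sentence have no start-date test, and the intercurrent-event rule counts all events. This stands in part: a reader might infer certain exclusion, but the section contradicts itself. The intercurrent-event rule does not settle the matter, since it deals with early discontinuation and not with onset. The variable, the TEAE definition and Section 6 all point to exclusion.

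A reader might also infer that the event disappears from the report. It does not. The all-AE table, the table of AEs leading to death and the SAE listing in SAP 3.4.2 are not restricted to TEAEs, and SAP 3.4.3 shows laboratory values by visit. With about 18 patients and no formal testing, each case can be seen.

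A third tempting reading is that the AESI endpoint is equally exposed, for example through mild screening anemia. The documents do not support that. The AESI needs hemoglobin below 10 g/dL together with reticulocytes below 50% of the Screening Visit 2 value, confirmed by repeat testing. Hemoglobin below 10.0 g/dL is an exclusion criterion. The full definition would ordinarily first be met after dosing, and nothing tells sites to give it the start date of a milder AE.

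Finally, Protocol 8.1 can be read more widely: it mentions signs present at baseline, and its laboratory paragraph covers significant findings detected during the study. eCRF completion instructions and programming specifications, which are not among the documents, might require a new record on worsening. That is possible, but a primary endpoint should not depend on an unstated convention.

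**Conclusion.** The point holds for the primary SAE endpoint, the TEAE tables and the TEAE-based laboratory endpoint. The start-date rule leaves out an AE that begins between consent and first dose and worsens or becomes serious on drug, while the summary measure would count one that becomes serious. The effect on the AESI endpoint is limited.

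One affected patient moves the primary percentage by 8.3 points (setanaxib) or 16.7 points (placebo) at 12 and 6 patients per arm. How often this would happen cannot be derived from the documents. The analyses are descriptive, so no error rate is affected.

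The conclusion assumes that a worsening AE keeps its original record and start date, as Protocol 8.1 and 8.3.2 suggest. If site instructions require a new record on worsening, the practical loss goes away, but the inconsistent wording in SAP 3.4.1 remains. This should be corrected before database lock.

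**What to change.** In SAP 3.4.1, define TEAEs as AEs that start on or after the first dose, or that start before it and increase in severity or become serious on or after it, up to 30 days after the last dose. Limit the pre-treatment category to AEs that start before the first dose and do neither. Then make the variable, summary-measure and presentation wording in 3.4.1 refer to the same set of events.

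The cost is a short text change and one derivation in the AE dataset. It would be wrong to assume that no new data are needed, because neither document shows that the eCRF holds the date on which severity rose or seriousness began. If it does not, add an instruction to record that date, or to open a new AE record on worsening, and query any AE with onset before first dose that was still ongoing at dosing.
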